## **2.3 Potential Risks**

### **Questionnaires and SMA Visit**

As part of the study, participants will participate in SMA and complete validated questionnaires which include questions about their private attitudes, feelings and behavior regarding the management of diabetes. It is possible that some people may find these discussions and/ or questionnaires to be mildly upsetting, however these questionnaires have been used in previous research and these types of reactions have been uncommon. Participants who are upset or worried after completing questionnaires

or participating in the study will be referred to our diabetes psychology team for additional support.

### **Privacy Concerns**

Data downloaded from the CGM will be collected for the study as measures of diabetes self-management behaviors. Some people may be uncomfortable with the researchers' having such detailed information about their daily diabetes habits, however this too is part of routine diabetes care. The group setting of the SMA removes much of the privacy that is provided to patients and their families during a routine individual visit. Some families might feel uncomfortable talking about personal experiences or attitudes related to their own diabetes care in front of other people. Description of the SMA will be clear during the consent process so that only families who are comfortable sharing in a group setting will choose to participate in the study. Participants and their caretakers will also have the option to withdraw from the intervention at any time if they become uncomfortable with the lack of privacy in the SMA.

### **Other Risks**

Some participants may develop skin irritation or allergic reactions to the adhesives used to secure the CGM. If these reactions occur, different adhesives or under dressings will be tried (such as with IV 3000, Tegaderm, etc.), sites will be rotated more frequently, and a mild topical steroid cream may be required.

Many of the risks associated with participation in this study are the same risks facing all patients receiving routine clinical care for T1D. Patient's diabetes data is routinely downloaded as a part of clinical care and is done in compliance with Health Insurance Portability and Accountability Act (HIPAA) regulations. While there is concern that the questionnaires may be upsetting to some participants, these types of reactions are rare and there are psychology staff available in our clinic should these types of reactions occur. The potential benefits for improvements in glycemic control and health-related quality of life far outweigh the minimal risks.

## **2.4 Potential Benefits**

The purpose of this study is to reduce healthcare disparities, promote technology uptake, and improve the glycemic control in underserved youth with T1D. Improvements in glycemic control may reduce both short-term risks of T1D, including hypoglycemia, hyperglycemia, and DKA, and the long-term risks of T1D, including nephropathy, neuropathy, retinopathy, cardiovascular disease, and neurocognitive dysfunction. The SMA visit structure may also have benefits on health related quality of life for youth and their caregivers. It is expected that the results of this study will inform the design of future randomized controlled studies that have the potential to alter future provider practices and reduce healthcare disparities.

## Section 3: Objectives and Endpoints

### 3.1 Primary Objective(s)

To evaluate the feasibility and acceptability of SMA among underserved youth with T1D as measured by recruitment, CGM initiation, retention, satisfaction surveys, and semi-structured interviews.

### 3.2 Secondary Objective(s)

To evaluate the preliminary impact of SMA on glycemic control, self-management skills, self-efficacy, diabetes related quality of life, and treatment satisfaction among underserved T1D youth, as measured by CGM data, and a battery of validated survey measures completed by the youth and their caretaker.

### 3.3 Primary Outcome Measure(s)

Given the novelty of the SMA approach for underserved youth and promotion of CGM technology uptake and sustained use, feasibility and acceptability of the intervention will serve as the primary outcome measure. We will track recruitment, enrollment, participation, and retention through a CONSORT table (Table 2) for the intervention group. Feasibility benchmarks include: recruitment (>60% of reached/eligible

participants), CGM initiation, (>80%), SMA sessions attended (>80%), and retention (>80%). In addition, feasibility encompasses demographic characteristics of the enrolled sample, with enrollment and overall increased uptake of CGM among youth from historically underrepresented racial and ethnic backgrounds (Black race and/or Latinx ethnicity) and income levels. Attrition data and team feedback will help determine how recruitment rates may be improved. Acceptability will be assessed using satisfaction surveys and determined by a high level of satisfaction with participation, perceived utility of the intervention content, and perceived benefit from participation (>80% reporting that they were satisfied and perceived utility and benefit). We will report summary statistics on each feasibility and

acceptability item in the questionnaires (mean and standard deviation as well as percent answering a specific Likert level). Acceptability also will be examined by key demographic characteristics, including participant age and race/ethnicity.

Parent-child dyads will participate in semi-structured interviews to assess satisfaction with the SMA. Thematic analysis of qualitative data will be conducted by two team members who will independently review interview transcripts to generate initial codes. Initial codes will be discussed by the group to generate a list of second-cycle codes and each team member will then apply the coding framework to all transcripts before

**Table 2.** Analytical plan for Aim 1, feasibility and acceptability.

Construct	Measure	Interval
Recruitment	# referred	Study initiation through completion of recruitment
Feasibility/	# screened	
Acceptability	# enrolled % eligible who enroll	
Intervention	#/% sessions attended	SMA visits every 3mo
Feasibility		
Intervention	Child/parent satisfaction ratings	After completion of intervention
Acceptability	Child/parent qualitative interview	
Retention	% who initiate CGM	All assessment time points
Feasibility/	% who continue on CGM	
Acceptability	% completing follow-up assessments	
Assessment	% participants with missing A1c data	All assessment time points
Feasibility	% participants with missing CGM data	
	% participants with missing survey data	

identifying dominant themes. ATLAS.ti software will be used to organize and analyze the qualitative data.

### **3.4 Secondary Outcome Measure(s)**

Secondary outcomes will include CGM metrics and chart review that can be used to assess effects on glycemic control, and survey measures designed to explore potential psychosocial benefits, including changes in self-management skills, self-efficacy, treatment satisfaction, and diabetes related quality of life. We will look at differences in the following measures from baseline to completion of the SMA intervention, as well as 3 and 6-months after completion of the SMA intervention: 1) CGM time in range from 70-180 mg/dL (TIR), 2) time below range (< 70 mg/dL) (TBR), 3) time above range ( $\geq$  180 mg/dL) (TAR), 4) mean sensor glucose, 5) coefficient of variation (CV) of glucose, 6) CGM wear time, 7) episodes of DKA, 8) episodes of severe hypoglycemia, 9) ED visits, hospital admissions, 10) A1c, 11) qualitative measures exploring self-management, satisfaction, health related quality of life as measured with the following validated questionnaires (T1DAL, DSMP, SEDS, C-PAID, CGM Benefits and Burdens scale).

CGM time in range from 70-180 mg/dL (TIR) has been correlated with A1c values, which have classically been used as primary outcomes in T1D studies because of their association with microvascular complications. This connection to long-term complications also makes TIR a better primary outcome measure than survey measures because this data has greater potential to alter real-world prescribing practices than patient perceptions captured by questionnaire. We have chosen to focus on TIR rather than A1c because of the propensity for A1c variation in Non-Hispanic Black youth who also have a higher propensity for hemoglobin variants.

Additional CGM derived measures of glycemic control are commonly used outcomes in studies of T1D technology. A1c has been included because it has classically been considered the gold standard. The acute complications of T1D being examined are also frequently used in T1D studies. The survey measures exploring quality of life are among the most widely accepted outcome measures in their specific topic areas.

## **Section 4: Study Design**

Dyads of youth with T1D aged 8-12 years and their primary diabetes caretakers identifying as non-Hispanic Black or Latinx will be recruited to participate in a prospective cohort pilot study exploring feasibility and acceptability of SMA and the impact on glycemic control, self-management skills, and health related quality of life. This trial will employ an enrollment visit, SMA visits every 3 months over a 12-month study period, and a follow-up 6-month observational period to continue to evaluate outcomes once patients return to routine individual follow up care. The study will include a single intervention group participating in the SMA visits (n=20).

All staff participating in the SMA visit will receive comprehensive training on how to facilitate the SMA discussion sessions effectively. All topics that will be covered at each SMA visit will be reviewed by the study staff ahead of the visit. Potential participants will

be screened for participation using our electronic medical records system and will be approached during routine clinical visits. After explaining all study procedures, informed consent using an IRB-approved consent form will be obtained for all participants. After obtaining consent, a blinded Dexcom G6 CGM will be placed on the participant. Participants will be instructed to wear the blinded CGM for 10 days in order to obtain baseline glycemic control data prior to starting the SMA visit intervention. At the completion of the 10 day wear period, participants will mail back the blinded CGM in a pre-addressed envelope so that the data can be assessed within 30 days of the wear time. Because SMA visits will be used in place of routine clinic visits and because participants will not require any additional in person study visits, we anticipate significant interest in participation with minimal barriers. Secure REDCap surveys will be sent to participants via email 1 week before each follow-up visit. If the surveys have not been completed at the time of the visit the participant will be asked to complete the measures using an iPad or paper in clinic at the time of their visit. Youth who elected not to use a CGM for routine clinical care, will be asked to wear a blinded professional CGM for 10 days prior to each visit whenever possible.

SMA Structure: SMAs will consist of 4-6 underserved youth with T1D and their primary diabetes caregiver. All youth and caretakers will complete standard check-in procedures with the clinic medical staff, including routine clinical intake questionnaires, vital sign assessments and point-of-care fingerstick A1c measurements. Before each session, dyads will be invited to submit questions to the research team that will then be anonymously reviewed and discussed among the group during the SMA. In the event that no questions are submitted by families, the facilitator will begin the discussion with stories and questions related to technology use and potential barriers in order to focus the discussion on the aspect of diabetes management being highlighted in that specific SMA. After discussing the questions, the facilitator will lead a group discussion focusing on the topic of the day. During each visit, the facilitator role will be shared by a pediatric endocrinologist, CDCES, nutritionist, and psychologist. Youth and caregivers will individually meet with the endocrinologist at different time points during the session to update personal management plans and goals of care. The group visit will conclude with a review of the core concepts discussed. Youth will be encouraged to set and share individual goals to be addressed before the next SMA.

Enrollment visit: This visit will occur at a routine clinic visit once a patient expresses interest in participating in the study. Alternatively, patients expressing interest in enrolling who are unable to do so at a routine clinic visit will have the option to come back for enrollment at a different time. A study team member will meet with the patient and family to review the study details and obtain consent. Randomization will be completed after consent has been obtained. A blinded Dexcom G6 pro CGM will be placed on the patient and be worn for 10 days in order to collect baseline data prior to starting the intervention. Phone applications that will allow for sharing of CGM data between patients and the diabetes clinical care team will be downloaded and established before the end of the visit.

**Initial SMA:** The structure of the group visits will be reviewed with patients and families, and all members of the diabetes team will introduce themselves and explain their role in diabetes care. As some patients will be CGM naïve before this visit, education will focus on insertion and removal of the CGM along with appropriate use of the CGM receiver, alerts and alarms, data sharing, and troubleshooting common CGM problems. Established sharing of CGM data between patients and the diabetes clinical care team will be confirmed before the end of the visit. The group visit will conclude with a review of the core concepts discussed, and patients will set goals for the next SMA.

**Follow Up SMA:** Follow up SMA will be scheduled 3, 6, 9, and 12 months from the initial group visit. CGM data from 14 days prior to each SMA will be reviewed by the endocrinologist ahead of the group visit. Discussions and education guided by the facilitators will focus on issues that have been described in the literature as potential barriers to CGM use and adherence. Recurrent alerts and alarms can result in alarm fatigue, and falsely low glucose readings and sensor or transmitter failures have been cited as reasons for discontinuing CGM use. The continuous nature of CGM data has been shown to place significant demands on patients and their families, and to create stress related to the constant need for diabetes-related attention. Follow up visits will focus on optimized use of CGM alarms and prevention of alarm fatigue. Psychologists and CDCES will discuss strategies to cope with the on-body presence and potential embarrassment resulting from CGM wear and to optimize parent-child communication surrounding CGM. Nutritionists will highlight the impact of different foods on glycemic trends and discuss strategies to optimize control. SMA will also allow ample opportunity to jointly review de-identified CGM reports and how to effectively interpret data and make management changes in response to CGM data, empowering patients and families to improve self-management and reduce stress related to CGM use. Active participation in discussions and group exercises will continue to strengthen the community feeling and social support network within the SMA group. Any participant that chooses to discontinue CGM during the 12 month study period will wear a blinded CGM 10 days prior to the follow up visits to allow for complete data collection. Upon completion of the final SMA visit at month 12, dyads will be contacted to schedule a semi-structured interview and will then return to standard clinical care.

**3-Month and 6-Month Post-Intervention Follow-Ups:** Survey measures and assessments of glycemic control will be repeated after 3 months and 6 months of routine clinical care to assess for long-lasting effects of the intervention.

## **Section 5: Study Enrollment and Withdrawal**

### **5.1 Study Population, Recruitment and Retention**

We propose to recruit up to 20 dyads of underserved children with poorly controlled T1D and their primary diabetes caregiver who express an interest in starting CGM therapy. We aim to recruit children with T1D ages 8-12 with T1D duration for at least 1 year, at least one A1c value > 8% in the past year, Black race and/or Latinx ethnicity, public health insurance, and English fluency in the youth and parent. The lower limit of the age inclusion criteria was selected so that patients will be able to fully participate in the SMA visits. The inclusion criteria were selected in order to demonstrate the effects that that

CGM technology can have in patients who are the least likely to have access to diabetes technologies.

Potential participants will be screened for participation using our electronic medical records system of the diabetes outpatient clinic, in accordance with the HIPAA rules. This study will include the vulnerable study population of children aged 8-12 years old, however no special considerations will need to be taken given that there is no greater than minimal risk with study participation. Parents/guardians will have access to the results of the children's participation once the study has been completed, as to not bias results while the intervention is still ongoing.

Eligible participants will be approached to participate during routine clinic visits after discussion with their primary endocrine clinician. For patients who cannot be approached in person at the time of the visit, we will attempt to contact individuals by email or phone. The email will include an option to opt-out of further contact. If a cellphone number is listed, the study team will also send a text (using a study designated number) after attempting to call. If an email address is not on file, a letter will be sent via mail. The text will not contain PHI and provides general information about the project and encourages those interested to respond and talk via phone. Patients and families who are still considering whether to enroll after the clinic appointment will be contacted by phone or text message after the visit. Participants will be offered parking or transportation reimbursement for each of the group clinic visits, and \$20 at each of the visits as well as at the 3-month and 6-month post intervention visit for completion of survey measures, regardless of if a patient withdraws early. Non-English speaking individuals will be excluded as the Dexcom CGM technology is currently available only in English.

## **5.2 Inclusion Criteria**

In order to be eligible to participate in this study, an individual must meet all of the following criteria:

1. Patients clinically diagnosed with T1D managed with insulin injections for at least 1 year
2. Non-Hispanic Black or Latinx ethnicity
3. Public healthcare insurance
4. Male or female ages  $\geq 8$  and  $\leq 12$  years
5. No prior use of CGM within 60 days of enrolment
6. Poorly controlled T1D: one A1c value  $> 8\%$  in the preceding year
7. Fluent in English as the Dexcom technology is currently available only in English
8. Participation of the primary diabetes caregiver

## **5.3 Exclusion Criteria**

An individual who meets any of the following criteria will be excluded from participation in this study:

1. Use of insulin pump therapy for diabetes management at time of enrolment
2. Major illnesses other than T1D
3. Significant cognitive limitations and major psychiatric disorders in the child or parent

4. Concurrent use of any non-insulin diabetes medication to control blood glucose levels.
5. Concurrent participation in any other clinical studies during study period

#### **5.4 Vulnerable Subjects**

This research will involve the federally recognized vulnerable subject population of children. As this research will not involve greater than minimal risk, no special considerations will need to be taken. Adequate provisions will be made for soliciting the assent of the children and the permission of their parents or guardians.

#### **5.5 Recruitment**

All patients scheduled for routine clinical diabetes appointments at Children's National Specialty Care Locations will be screened through chart review by study team members to assess for eligibility after a HIPAA authorization waiver for recruitment is granted. We anticipate enrolling 5-7 patients per month over 3-4 months to meet our target enrollment of up to 20 participants. Patients will be approached to participate during routine clinical visits. For patients who cannot be approached in person at the time of the visit, we will attempt to contact individuals by email or phone. The introductory email will be co-signed by the PI and [name], CNH Child and Adolescent Diabetes Program. The email will include an option to opt-out of further contact. If a cellphone number is listed, the study team will also send a text (using a study designated number) after attempting to call. If an email address is not on file, a letter will be sent via mail. The text will not contain PHI and provides general information about the project and encourages those interested to respond and talk via phone. Patients and families who are still considering whether to enroll after the clinic appointment will be contacted by phone or text message after the visit. Once a potential participant has been identified, a study team member will give an IRB approved study information letter to the participant's legally authorized representative (LAR). If the LAR expresses interest in the study, a copy of the IRB approved consent will be provided to the LAR. The informed consent will be signed by the LAR and assent will be obtained from the patient at an in-person visit before any research interventions are done. For patients who cannot be approached in person at the time of the visit, we will attempt to contact individuals by phone and obtain e-consent and/or e-assent with REDCap. The REDCap link of the IRB approved consent will be provided to the LAR via text or email. The informed consent will be electronically signed by the LAR and assent will be obtained electronically from the patient. All study team pre-screening materials that contain patient information will be maintained on password protected computers. Only authorized team members will have access to the pre-screening materials, Any pre-screening PHI that was collected will be destroyed once study enrollment has been completed.

#### **5.6 Retention**

To enhance participant retention, we will obtain multiple methods for contact for participants and their parents. Patients and parents will receive reminders- via email, text, and/ or phone call as per participants' preference to alert them to upcoming SMA visits. Participants will also receive reimbursement for transportation or parking.

Participants who complete the survey measures will be compensated with \$20 at the baseline and for each follow-up visit. If a participant unexpectedly misses an in-person SMA visit, the participant's legally authorized representative will be contacted by a member of the study team to check on the participant's welfare and to see if there are any barriers to the participant attending future group sessions. Efforts will be made to have participants join an alternative session to make up for any missed scheduled SMA sessions.

### **5.7 End of Participation Criteria and Procedures**

Participants are free to withdraw from participation in the study at any time upon request. The reason for participant discontinuation or withdrawal from the study will be recorded on the Premature Termination Case Report Form (CRF). Subjects who sign the informed consent but do not receive the study intervention may be replaced. Subjects who sign the informed consent form, begin the study intervention, and subsequently withdraw, or are withdrawn or discontinued from the study, will try and be replaced.

Participants who experience significant psychological distress as a result of the intervention or whose presence at SMA visits will be terminated from study participation. Anyone experiencing psychological distress will be referred to the diabetes psychology team for support (Drs. [name] and [name], Co-I's).

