If a visit is missed by the participant, he/she will have the option to attend a different group's SMA that corresponds to the same timing as the SMA that was missed. In the event of withdrawal or early termination, participants will be asked to come for an end of study visit. If any participant chooses to discontinue CGM use, they will be asked to wear a blinded CGM for each of the 10 day periods ahead of their planned clinic visits.

Upon completion of the final SMA visit at month 12, dyads will be contacted to schedule a semi-structured interview and will then return to standard clinical care. A structured focus group guide consisting of broad, open-ended questions to elicit details from patients and parents will be provided to facilitators. These sessions will last 45 minutes ( $\pm$  15 minutes). The sessions will be recorded on two separate devices and subsequently transcribed to allow for data analysis.

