### **8.2 Statistical Hypotheses**

Primary Outcome: feasibility and acceptability of SMA among underserved youth with T1D.

Hypothesis 1a. Rates of SMA retention (>80%) at 12-months and satisfaction with visits (>80%) will be high.

Null Hypothesis 1a: n/a

Hypothesis 1b: Thematic analysis of semi-structured interviews will identify high satisfaction with SMA.

Null Hypothesis 1b: n/a

Secondary Outcome: preliminary impact of SMA on glycemic control, self-management skills, self-efficacy, diabetes related quality of life, and treatment satisfaction among underserved children with T1D and their caregivers

Hypothesis 2a: CGM percentage wear time and sustained use, as defined by use within the 2 weeks prior to the visit, will be greater upon completion of the SMA intervention at 12 months compared to baseline

Null Hypothesis 2a: CGM percentage wear time and sustained use, as defined by use within the 2 weeks prior to the visit, will not be significantly different upon completion of the SMA intervention at 12 months

Hypothesis 2b: CGM time in range (70-180 mg/dL) will be greater and the glucose management indicator (GMI) lower for youth upon completion of the SMA intervention group at 12 months compared to baseline.

Null Hypothesis 2b: CGM time in range (70-180 mg/dL) will not be significantly different upon completion of the SMA intervention at 12 months

Hypothesis 2c: Diabetes-specific quality of life, self-management behaviors, and self-efficacy scores will be greater upon completion of the SMA intervention at 12 months compared to baseline.

Null Hypothesis 2c: Diabetes-specific quality of life, self-management behaviors, and self-efficacy scores will not be significantly different upon completion of the SMA intervention at 12 month

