### **8.3 Analysis Datasets**

Data analysis will be conducted according to a per-protocol analysis as we will be unable to obtain appropriate data from those who withdraw from the study. Participants with incomplete data will be included in analyses when possible.

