## **8.5 Sample Size**

As this is a pilot study, we plan to enroll up to 20 parent-child dyads. We anticipate low dropout rates, but do plan to enroll new subjects to keep the total number of subjects at up to 20 in case of attrition. If there is a sufficient number of new subjects enrolled to replace those that drop out, a new SMA group will be created so that newly enrolled subjects will be able to start the intervention from the baseline visit.

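### Section 5.7 ends study participation, not only SMA attendance, for distressed participants; any such exits could tilt the acceptability result toward families who tolerated the groups

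*Combined protocol and SAP*

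**What the plan says.** **Exit rule.** Section 5.7: "Participants who experience significant psychological distress as a result of the intervention or whose presence at SMA visits will be terminated from study participation". The second ground lacks a predicate, so its meaning is unclear; the distress ground is clear. The same section refers distressed participants to psychology, records the reason for any exit on a case report form, and aims to replace people who leave after starting.

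**Replacement.** Section 8.5: "If there is a sufficient number of new subjects enrolled to replace those that drop out, a new SMA group will be created". Section 4 gives the group size: "SMAs will consist of 4-6 underserved youth with T1D and their primary diabetes caregiver".

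**What is collected from leavers.** Section 6.3: "In the event of withdrawal or early termination, participants will be asked to come for an end of study visit". The content of that visit is not specified. Section 2.3 (Privacy Concerns) separately gives families the "option to withdraw from the intervention at any time if they become uncomfortable with the lack of privacy in the SMA", with no assessment schedule afterwards.

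**When acceptability is measured.** Table 2 in Section 3.3 puts child and parent satisfaction ratings and the interview after the intervention is complete. Section 6.3 arranges the interview after the month-12 SMA. Table 1 and Section 6.4 also schedule an SMA evaluation, from child and caregiver, at every visit.

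**Benchmark and analysis set.** Hypothesis 1a in Section 8.2: "Rates of SMA retention (>80%) at 12-months and satisfaction with visits (>80%) will be high". No null hypothesis is attached. Section 6.4 counts a rating of 4 or 5 as satisfied. No section says whether the denominator is starters or completers, or whether dyads or persons are counted. Section 8.3 specifies a "per-protocol analysis as we will be unable to obtain appropriate data from those who withdraw from the study" and then adds: "Participants with incomplete data will be included in analyses when possible".

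**The concern.** Acceptability is part of the primary outcome, and the trigger for this exit is harm from the intervention whose acceptability is being judged. Participants removed on that ground are plausibly less satisfied than those who stay, and the rule ends their participation before the Table 2 rating and the month-12 interview. The per-protocol set and the replacement rule then act in the same direction. Section 8.6 names no measure against bias.

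The reason that 8.3 gives for a per-protocol set is that usable data cannot be had from people who withdraw. For these families that is partly the protocol's own doing. They need not have refused follow-up, and A1c, clinical CGM and chart data arise in the routine care to which the child returns. At stake is whether the acceptability figure carried forward to later randomized studies describes everyone who started the groups or mainly those who could tolerate them.

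**Working it through.** The plan has no figure of its own to reproduce: 20 dyads is a pilot choice, and no termination or dropout rate is stated. The steps below illustrate how sensitive the benchmark is; they do not predict a result.

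**Inputs.** N = 20 dyads, the ceiling in 8.5. The pass mark is above 80% (3.3, 8.2). The number of dyads terminated for distress, k, is assumed to be 0 to 3. Terminated dyads are assumed unsatisfied, unrated and not replaced.

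**Formulas.** With s satisfied dyads among those who remain, completers pass if s/(20 − k) > 0.80. All starters pass if s/20 > 0.80, that is, s ≥ 17.

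| k | Raters | Smallest passing s | Share of raters | Same s as share of 20 | Values of s at which the result changes |
|---|---|---|---|---|---|
| 0 | 20 | 17 | 85.0% | 85.0% | none |
| 1 | 19 | 16 | 84.2% | 80.0% | 16 |
| 2 | 18 | 15 | 83.3% | 75.0% | 15, 16 |
| 3 | 17 | 14 | 82.4% | 70.0% | 14, 15, 16 |

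If every remaining dyad is satisfied, nothing changes: 19/20, 18/20 and 17/20 all exceed 80%.

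**Counting persons (40).** Starters need 33/40 (82.5%). At k = 1 there are 38 raters, and the result changes at 31 (31/38 = 81.6%, 31/40 = 77.5%) and at 32 (32/38 = 84.2%, 32/40 = 80.0%). If only the child of the terminated dyad is unsatisfied, starters pass if (s + 1)/40 > 0.80. The result then changes at 31 only, where (31 + 1)/40 = 80.0%.

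**If the leaver's rating is obtained.** At k = 1, s = 16, a recorded unfavourable rating restores 16/20 = 80.0% and the gap closes. The effect therefore depends on leavers being unrated.

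**Does the retention benchmark flag it?** Not in this range. At k = 3 retention is 17/20 = 85.0%, which passes; it fails at k = 4 (16/20 = 80.0%).

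**Replacement.** This is not modelled, because one to three terminations alone would not fill a group of four to six. If two terminated dyads were replaced together with other leavers, 17/20 = 85.0% of completers would be 17/22 = 77.3% of those dyads plus the two terminated.

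**Later outcomes.** Table 1 has seven assessment points. Exit after the Initial SMA leaves six unobserved, or five if the end-of-study visit is a full assessment. Exit after month 6 leaves four, or three.

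**Cause.** Nothing in these formulas refers to distress. The same shift arises from k dyads lost for any reason if they are unsatisfied and unrated. What 5.7 adds is an exit that the protocol imposes and that is tied to a bad experience of the groups.

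**The case against.** The strongest reply is that 5.7 is not the main source. The pass/fail shift is a denominator effect that comes from 8.3 and the undefined acceptability denominator. Repairing those two would remove most of it without touching 5.7. This stands, and it sets the order of the fixes.

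Second, the unrated assumption is a worst case. Child and caregiver SMA evaluations are scheduled from the Initial SMA onward, an end-of-study visit is requested, and incomplete data may be used. Section 5.1 also ties survey payments to completion even after early withdrawal, which may mean that surveys after exit are contemplated, or only that earned payments are kept. A reader might infer that leavers would have no ratings at all; the documents do not show that. They also do not say that earlier or exit ratings count toward the benchmark, so the possible loss remains.

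Third, ending research participation for a significantly distressed child aged 8 to 12 is a defensible welfare choice, because 2.3 and 7.1 name questionnaires as a source of distress. This too stands. The contrast with children who stop CGM, whom 6.3 keeps under assessment, is imperfect, since stopping a device is not psychological harm. Any follow-up must be optional, and the clinical decision stays with the investigators.

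Fourth, exits would be visible in the CONSORT table, the termination form and the individual listings, and an exit for intervention-related distress is itself a negative signal. That is true, but it shows that a dyad left and why, not how it rated the groups.

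**Conclusion.** The point holds in a limited form. Followed as written, the plan would select the acceptability result toward families who tolerated the groups whenever someone is terminated for distress. With at most 20 dyads, one such exit can decide the benchmark: 16/19 (84.2%) against 16/20 (80.0%). That figure assumes one dyad leaves, is unsatisfied, has no usable rating and is not replaced. With no exits, or with ratings recovered, the effect is absent or smaller.

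A reader might infer that the results are likely to be biased, or that 5.7 alone produces the shift. The documents support neither. They give no termination rate, describe risk as minimal (7.1), upset reactions as uncommon (2.3) and dropout as low (8.5), and the denominator mechanism is common to all attrition. The benchmark is also descriptive, with no null hypothesis or progression rule, so the consequence is a less interpretable acceptability figure rather than a wrong formal decision. The direction is clear, the frequency is unknown, and the repair is cheap enough to make.

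**What to change.** 1. Amend 8.3 to analyse all available data from every dyad that started the SMA. Keep discontinued and replaced dyads in the retention and acceptability denominators, and state whether acceptability is counted by dyad or by person.
2. At the end-of-study visit in 6.3, collect the existing SMA satisfaction rating and offer the interview to anyone who stops SMA for any reason, including the privacy withdrawals in 2.3. Extend the Table 2 interval to cover SMA discontinuation as well as completion. If the visit is declined, use the last SMA evaluation, noting that it may predate the distress.
3. Report acceptability also with unrated starters counted as not satisfied.
4. In 5.7, end SMA attendance rather than study participation. Allow continued use of routine-care A1c, clinical CGM and chart data, strictly optionally, with caregiver consent and child assent. Leave the clinical decision with the investigators. Complete or delete the unfinished second ground.

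**Cost.** One IRB amendment covering protocol, consent and assent wording, and a little staff time for exit interviews (6.3 plans 45 ± 15 minutes each, with transcription). No new instrument is needed. Some families will decline, so selection is reduced but not removed.
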